7.1 Background

Atrial fibrillation (AF) is a heart rhythm disorder caused by abnormal electrical signals from the atria and is characterized by ineffective atrial contraction and irregular heartbeats. AF can occur in three forms: paroxysmal (episodes lasting less than 7 days), persistent or permanent (lasting more than 7 days) and irreversible (1).

Among patients with AF, more than one-third have associated valve disease, characterized by mitral stenosis or valve prosthesis (1). In this case, AF is called "valvular" (2). Conversely, in patients without associated valvular pathology, AF is said to be "non-valvular".

In France, two-thirds of AF patients are 75 years of age and older. The prevalence of AF is about 1% of the general population and increases with age to reach 10% of the population aged 80 years and over. The male/female sex ratio of prevalent cases is 3:2 (3). The absolute number of cases is equivalent between men and women because of the higher life expectancy in women (4).

Several pathophysiological mechanisms, including blood flow stasis, prothrombotic state, and hypercoagulability induced by AF, can lead to stroke (5). Clinical signs may include shortness of breath at rest, fatigue, palpitations, or chest pain. AF accounts for approximately 15% of all strokes (6).

The therapeutic management aims to prevent thromboembolic complications (risk multiplied by 5), in particular the occurrence of ischemic stroke, to reduce symptoms, to prevent recurrence of AF using antiarrhythmic treatment and to improve the quality of life of patients (4). The 2014 Guidelines of the French National Authority for Health recommend initiating an oral anticoagulant (OAC) in AF patients to prevent the risk of stroke in the event of a high thromboembolic risk identified by a CHA2DS2-VASC score greater than or equal to 2. If the score is equal to 1, the initiation is to be discussed according to risk factors. Among the OACs, the antivitamins K (VKA) (warfarin, acenocoumarol – and fluindione until 2017) were considered as the reference drugs until 2017; the direct oral anticoagulant (DOAC) including direct factor Xa inhibitors (rivaroxaban and apixaban) and direct thrombin inhibitor (dabigatran) could be prescribed as an alternative (4). Recommendations concerning the good use of OACs has been updated in 2018 (5). **Since then, DOAC can also be prescribed as a first-line treatment in non-valvular AF (NVAF) patients.**

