9.4.3.2 Comparison of the incidence of stroke, major bleeding, death

The incidence rate ratio for each event of interest (stroke, major bleeding and death; see [Table VIII](#) for derivation of events of interest) will be compared using a Cox regression model with OAC exposure (see [Table VII](#) for derivation of exposure sequences) considered as time-dependent variable adjusted for covariates. Covariates will be derived at index date as indicated in [Table XV](#).

Table XV. Derived variables for confounders

Variable	Definition
Age	Categorical variable (<80 years old / 80–90 / >90 years old) See Table III
Sex	Binary variable (Female / Male) See Table III
Prescriber's specialty at initiation of OAC	Categorical variable (Hospital-based physician/ City cardiologist/ Generalist practitioners/Other) See Table III
Having Malnutrition	Binary variable (Yes / No) See Table III
Risk of falls	Binary variable (Yes / No) See Table III
Frail patients	Binary variable (Yes / No) See Table V
Morbid obesity	Binary variable (Yes / No) See Table VI
At least one visit to a nursing home	Binary variable (Yes / No) See Table VI
Concomitant treatments	Binary variable (Yes / No) for each concomitant treatment listed in Table XIV

For example, for antiplatelet drugs, equals to “Yes” if the patient has at least one reimbursement for an antiplatelet drug in the 4 months before the index date
	
HAS-BLED score	Categorical variable (0, 1, 2, 3, ≥ 4) See Table VI
CHAD₂DS₂VASC score	Categorical variable (0, 1, 2, 3, 4, ≥ 5) See Table VI
Age adjusted Charlson Cormordity Index (ACCI) adapted to SNDS data	Categorical variable (0, 1-2, 3-4, ≥ 5) See Table VI XII

9.4.3.3 *Estimation of the AF annual standardized incidence rate and prevalence*

All the variables in [Table XVI](#) will be derived for all AF patients in France in 2016, 2017, 2018 and 2019.

Table XVI. Derived variables for incidence and prevalence

Variable	Definition
Incident AF patient	Binary variable (Yes / No) See Table X
Prevalent AF patient	Binary variable (Yes / No) Equals to “Yes” if the patient is diagnosed AF during the historical period Patients belonging to the study population

9.4.3.4 *To describe the use of oral anticoagulants (OACs) in AF patients initiating treatment (AF patients exposed to OAC therapy)*

Table XVII. Derived variables for OAC treatment pattern

Variable	Definition

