9.7.4.2 Comparison of the incidence of stroke, major bleeding, death

Analyses will be performed independently for each event of interest stroke, major bleeding and death.

Survival analysis will be performed to compare incidence rate (stroke, major bleeding or death) in AF incident patients exposed and unexposed to OAC therapy **excluding those with a reported outcomes of interest up to 30 days prior index date**, using a Cox regression model. The Cox regressions models will consider the first event of interest occurring in AF incident patients exposed and unexposed to OAC. OAC exposure will be considered as time-dependent variable and the models will be adjusted for covariates defined below. By applying the OAC exposure variable as a time dependent variable, estimates of Hazard Ratio will account for switches and discontinuations. Time-dependent exposure Cox proportional hazards models will be used to estimate:

- The Crude hazard ratio (i.e. the incidence rate ratio), and therefore the risk of each outcome at any point during the follow-up since index date
- The adjusted hazard ratio on potential confounders including patient:
 - Time-fixed confounders: sex, age (<80, 80-90, >90 years old), prescriber's specialty at initiation of OAC, having malnutrition (yes/no), risk of falls (yes/no), morbid obesity (yes/no), history of stroke (yes/no), history of major bleeding (yes/no), at least one visit to a nursing home (yes/no), history of dementia (yes/no), concomitant treatments (e.g. receiving at least one antiplatelet drugs (yes/no), other anticoagulant drugs (yes/no), etc. - cf. *Table XV for all confounders*)
 - Time-dependent confounders: AOC treatment exposure

In a first model, patient exposure will be modelled according to five categories: exposure to apixaban, dabigatran or rivaroxaban, exposure to VKA or unexposed patients. In a second model, exposure to DOACs will be integrated instead of exposure to apixaban, dabigatran or rivaroxaban. For both models, the reference for comparison will be VKA exposure.

Same models will be performed on AF incident patients with a high thromboembolic risk (if modified CHAD₂DS₂VASC score is ≥ 2 for males and ≥ 3 females). Patient exposure will be modelled according to three categories: exposure to DOAC (Apixaban, Dabigatran or Rivaroxaban), exposure to VKA or unexposed patients. The reference for comparison will also be VKA exposure.

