9.7.6 Sensitivity analyses

We will perform the following sensitivity analyses:

1. Analyses on the evaluation of the incidence rate and comparison of the events of interest (stroke, major bleeding, and death) will be performed from the inclusion date for all incident AF patients (i.e. the inclusion date will be the index date for all incident patients, whether or not patients received OAC therapy within 30 days of the inclusion date).
2. Analyses including the 2020 data (given the uncertainty of the impact of the Covid 19 health crisis on the management of NVAF incident patients) will be conducted on:
 - Description of the follow-up of the study population (Table A1);
 - Sociodemographic characteristics (Tables A4 and A7), medical history and comorbidities (Table A5 and A8); concomitant treatments (Tables A6 and A9);
 - Estimation and comparisons of the incidence of interest-events in AF exposed and unexposed to OAC (primary objective - Table A2, secondary objective - Table A10);
 - Estimation of the annual incidence rate and the prevalence of AF patients (Tables A12 and A13 respectively).
3. Analyses on AF patients without the second inclusion criteria (new OAC users identified by the algorithm of *Billionnet et al.* not included) will be performed for the estimation of the annual standardized incidence and prevalence (Tables A12 and A13 respectively).
4. Analyses will be considered to test the impact of different grace periods (duration of 30 days and 90 days) in the calculation of treatment sequences for the following objectives:
 - Estimation and comparisons of the incidence of interest-events in AF exposed and unexposed to OAC (primary objective - Table A2, secondary objectives - Table A10)
5. If more than 10% of each event of interest occur during the 60 days grace period, analyses will be performed considering this event of interest in an unexposed period for the following objectives:

- Estimation and comparisons of the incidence of interest-events in AF exposed and unexposed to OAC (primary objective - Table A2, secondary objectives - Table A10)

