3.3. Comparison of the incidence of stroke, major bleeding, death

Table A10. Risk of stroke, major bleeding or death in AF incident patients

	Event		Crude risk ¹		Adjusted risk ^{2,*}	
	n	%	HR	[95%CI]	HR	[95%CI]
Risk of stroke						
Exposure to DOACs	xx	(x.x)	x.xx	[x.xx-x.xx]	x.xx	[x.xx-x.xx]
Exposure to Apixaban	xx	(x.x)	x.xx	[x.xx-x.xx]	x.xx	[x.xx-x.xx]
Exposure to Dabigatran	xx	(x.x)	x.xx	[x.xx-x.xx]	x.xx	[x.xx-x.xx]
Exposure to Rivaroxaban	xx	(x.x)	x.xx	[x.xx-x.xx]	x.xx	[x.xx-x.xx]
Unexposed to OAC**	xx	(x.x)	x.xx	[x.xx-x.xx]	x.xx	[x.xx-x.xx]
Exposure to VKA	xx	(x.x)	ref		ref	
Risk of major bleeding						
Exposure to DOACs	xx	(x.x)	x.xx	[x.xx-x.xx]	x.xx	[x.xx-x.xx]
Exposure to Apixaban	xx	(x.x)	x.xx	[x.xx-x.xx]	x.xx	[x.xx-x.xx]
Exposure to Dabigatran	xx	(x.x)	x.xx	[x.xx-x.xx]	x.xx	[x.xx-x.xx]
Exposure to Rivaroxaban	xx	(x.x)	x.xx	[x.xx-x.xx]	x.xx	[x.xx-x.xx]
Unexposed to OAC**	xx	(x.x)	x.xx	[x.xx-x.xx]	x.xx	[x.xx-x.xx]
Exposure to VKA	xx	(x.x)	ref		ref	
Risk of death						
Exposure to DOACs	xx	(x.x)	x.xx	[x.xx-x.xx]	x.xx	[x.xx-x.xx]
Exposure to Apixaban	xx	(x.x)	x.xx	[x.xx-x.xx]	x.xx	[x.xx-x.xx]
Exposure to Dabigatran	xx	(x.x)	x.xx	[x.xx-x.xx]	x.xx	[x.xx-x.xx]
Exposure to Rivaroxaban	xx	(x.x)	x.xx	[x.xx-x.xx]	x.xx	[x.xx-x.xx]
Unexposed to OAC**	xx	(x.x)	x.xx	[x.xx-x.xx]	x.xx	[x.xx-x.xx]
Exposure to VKA	xx	(x.x)	ref		ref	

AF : Non Valvular Atrial Fibrillation; HR: hazard ratio; 95%CI: 95% confidence interval

Note: For considering DOAC treatment in models, two regressions models will be performed for this table: one model with "Exposure to DOACs" as independent variable; second model with exposure for each molecule within the class of DOAC (Apixaban, Dabigatran, Rivaroxaban).¹From a time-dependant exposure to OAC Cox proportional hazards model

²From a time-dependant exposure to OAC and time-fixed covariates Cox proportional hazards model;

*Adjusted on the following covariates at index date: age (<80, 80-90, >90 years old), sex, having malnutrition, risk of falls, morbid obesity, history of stroke, history of major bleeding, at least one visit to a nursing home, history of dementia, each concomitant treatments

**Unexposed to OAC correspond to the period where the patients are not exposed to OAC.

Same table will be presented for sensitivity analyses:

- with integration of 2020 data

- with 30 days and 90 days of maximal number of days allowed for being refilled

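### The Cox models have no calendar-time term, so if the VKA/DOAC mix shifts over 2016-2019, part of any shared trend in event rates can be attributed to drug class.

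*SAP*

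**What the plan says.** **Time scale and reference.** SAP 9.7.4.2 describes the hazard ratio as reflecting "the risk of each outcome at any point during the follow-up since index date". Time zero is therefore the index date, and the baseline hazard absorbs follow-up time only. On the contrast: "For both models, the reference for comparison will be VKA exposure".

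**Covariates.** The text lists "Time-fixed confounders: sex, age (<80, 80-90, >90 years old), prescriber's specialty at initiation of OAC" and then other baseline characteristics. The time-varying line reads "Time-dependent confounders: AOC treatment exposure", which is the exposure itself. Section 9.4.3.2 says "Covariates will be derived at index date as indicated in" Table XV. That table adds frailty, HAS-BLED, CHA2DS2-VASc and the Charlson index. The footnote of Table A10 begins "Adjusted on the following covariates at index date: age (<80, 80-90, >90 years old), sex, having malnutrition, risk of falls, morbid obesity", and that of Table A11 gives the same list. None of these places contains index year, current year or a period indicator. Protocol 3.7.2.2 has none either.

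**Calendar span.** Inclusion runs over 2016-2019, extended to 2020 for sensitivity analyses (SAP 9.2.1.1). Calendar year is used in descriptive work: characteristics, annual incidence and prevalence, and resource use.

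**What the SAP says about 2018 and 2020.** Section 7.1 describes VKAs as the reference drugs until 2017 and, after the 2018 update, says: "Since then, DOAC can also be prescribed as a first-line treatment in non-valvular AF (NVAF) patients". Section 7.2 makes describing the resulting changes in management a purpose of the study. Section 9.7.6 adds 2020 as a sensitivity analysis, "given the uncertainty of the impact of the Covid 19 health crisis on the management of NVAF incident patients".

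**The concern.** At any given time since index, the risk set mixes patients who entered in different years. If VKA starts are concentrated in the earlier years, VKA person-time comes from earlier calendar periods than DOAC person-time at the same point of follow-up. Any change over the calendar that affects all patients alike (coding, acute care, background mortality) then differs on average between the two groups, and the model has no term to take it out. The unexposed-versus-VKA contrast is open to the same problem if the unexposed share drifts.

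No planned check would show this. The Schoenfeld residuals and log-log plots look at proportionality over follow-up time. The sensitivity analyses vary start date, data span, cohort definition and grace period, and none adjusts for calendar time. Table A10 with 2020 added is the same model. If it differs from the main result, the reader cannot tell a period effect from a change in exposure mix.

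**Working it through.** **Inputs from the documents.** Four entry years; VKA as reference; time scale since index; no calendar term; 225,747 new OAC users in 2018 (SAP 9.5). Over four years, 225,747 × 4 = 902,988 exposed patients. The plan states no bias figure to reproduce.

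**Assumed, because the documents are silent.** VKA share of starts by year, switching from VKA to DOAC, event rates and their trend. The ranges are shown below.

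**Hand check of the mechanism.** Take two equal entry cohorts with VKA shares 35% (2017) and 20% (2018). The true hazard ratio is 1, and event rates are 1 in the first cohort and 0.9 in the second for everybody.
- VKA mean rate: (0.35 × 1 + 0.20 × 0.9) / 0.55 = 0.9636
- DOAC mean rate: (0.65 × 1 + 0.80 × 0.9) / 1.45 = 0.9448
- Ratio: 0.9448 / 0.9636 = 0.980

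With a rise to 1.1 the same sum gives (1.53 / 1.45) / (0.57 / 0.55) = 1.018. With equal shares in both years the ratio is 1.

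**Full calculation.** Patients enter uniformly by month over 2016-2019 and follow-up ends in December 2019. Let N1(u), N0(u) be the DOAC and VKA numbers at risk at month u since index, summed over entry months, and D1(u), D0(u) the expected events when the true hazard ratio is 1. The model's limiting hazard ratio θ solves

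Σ_u { D1(u) − [D1(u) + D0(u)] · θN1(u) / (θN1(u) + N0(u)) } = 0.

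The base rate cancels. Switching is 0 or 20% of VKA patients per year from 2018. Values of θ:

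| VKA share 2016/17/18/19 | Switching | −10%/yr | −5%/yr | +5%/yr | +10%/yr | 10% fall in 2018 |
|---|---|---|---|---|---|---|
| 25% flat | 0 | 1.000 | 1.000 | 1.000 | 1.000 | 1.000 |
| 25% flat | 20% | 0.993 | 0.996 | 1.003 | 1.007 | 0.997 |
| 35/32/25/20% | 0 | 0.984 | 0.992 | 1.007 | 1.014 | 0.994 |
| 40/35/20/15% | 0 | 0.972 | 0.987 | 1.013 | 1.025 | 0.989 |
| 50/45/15/8% | 0 | 0.956 | 0.979 | 1.020 | 1.040 | 0.983 |
| 50/45/15/8% | 20% | 0.950 | 0.975 | 1.024 | 1.047 | 0.980 |

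**How much of a trend leaks in.** For the 10% fall in 2018, ln(0.9941)/ln(0.9) = 0.06 in the mildest shifting case and ln(0.9799)/ln(0.9) = 0.19 in the steepest. About 6% to 19% of the change, on the log scale, goes to drug class.

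**Against precision.** The information on the log hazard ratio is Σ D·p(1 − p), with D the events in a risk set and p its DOAC fraction. With 902,988 patients, shares 40/35/20/15%, 10% attrition per year and assumed rates of 1.5% (stroke), 3% (bleeding) and 8% (death) per year, the standard errors are about 0.014, 0.010 and 0.006. The 95% half-widths (× 1.96) are about 2.7%, 1.9% and 1.2%. For death, the 1.3% bias from a 5% annual trend in this share scenario is as large as the half-width.

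**Adding 2020.** With no trend to 2019, a shared 10% drop in 2020 and shares of 40/35/15/10/8% or 25/20/12/9/8%, θ lies between 0.984 and 0.989. The result moves through period alone.

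**With adjustment.** Stratified on index year, θ is 1.000 without switching and 0.998 to 1.002 with it. Stratified on current calendar year, θ is 0.995 to 1.005 for trends up to 10% per year and 1.000 for a step at a year boundary.

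**The case against.** The strongest case against is that every input that produces a bias is assumed. With a 1% annual trend, or a VKA share falling only from 15% to 10%, the effect is trivial: for that small share change without switching, the hazard ratio is 0.9992 to 0.9958 for trends of −1% to −5% per year. Baseline adjustment for CHA2DS2-VASc, HAS-BLED, Charlson index, frailty and concomitant drugs could absorb a trend that works through case mix, and the calculation has no covariates. The year most likely to be disrupted, 2020, is already outside the main analysis. The SAP plans hazard ratios with 95% intervals and no significance test on them, so a shift of 1% to 2% would not change a reading based on effect size. All of this stands as a limit on size. It does not supply the missing term, and no planned analysis adjusts for calendar time.

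Two stronger readings are tempting. A reader might infer that the SAP reports prescribing as having moved from VKA to DOAC in 2018. It does not: section 7.1 reports what may be prescribed, gives no share by year, and leaves the change in management for the study to describe. The shift is a reasonable expectation only. A reader might also infer that any calendar change is credited in full to DOACs. It is not: only a fraction leaks in, none when the mix of person-time is constant, and rising rates would favour VKA.

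**Conclusion.** The omission is certain; it can be read directly from 9.7.4.2, Table XV and the footnotes of Tables A10 and A11. The bias is conditional on a shift in the VKA/DOAC mix and on a trend in event rates not captured by the baseline covariates, and its direction cannot be known in advance. Under the assumed ranges it is about 0 to 2.5% on the hazard ratio for trends up to 5% per year, and about 5% at 10% per year with the steepest share change and switching. That is modest. It deserves correction because the cohort is large enough for biases of this size to rival the confidence interval, and because the 2020 analysis cannot be interpreted as planned.

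**What to change.** In SAP 9.7.4.2 and Table XV, state that the baseline hazard of every Cox model is stratified on calendar year of index date. Apply this to Tables A10 and A11 and their sensitivity versions, and amend the footnotes. Patients are then compared at the same follow-up time within the same entry year, so their calendar dates differ by less than a year.

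As an alternative, enter current calendar year as a time-varying categorical term. The two are not identical, but both remove nearly all the bias. Current year has the advantage that it also serves as the Covid-period term when 2020 is included. If the Aalen model is used as the fallback, enter calendar year there as a covariate.

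The cost is one sentence and one STRATA statement; index year is already needed for Tables A4 to A6. From the information formula above, standard errors rise by about 3% or less in most assumed cases (for stroke with shares 40/35/20/15%, 0.0138 to 0.0140). The rise is nearer 5% with shares 50/45/15/8% (0.0134 to 0.0140), which is also where the unadjusted bias is largest.

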8.2 Secondary Objectives

2. To describe the characteristics of non-valvular AF patients exposed and unexposed to OAC
3. To compare the incidence rate of stroke, major bleeding, and death between those two populations
4. To estimate the annual incidence and prevalence of patients with non-valvular AF, exposed and unexposed to OAC
5. To describe the use of oral anticoagulants (OACs) in non-valvular AF patients initiating treatment (AF patients exposed to OAC therapy)
6. To compare Healthcare Resource Utilization (HCRU) and associated costs between patients exposed to apixaban, rivaroxaban, dabigatran, VKA and patients unexposed to OACs
7. To describe the therapeutic management before/after the first stroke occurring after initiation of OAC exposure

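### All planned Cox models use VKA as reference, so the adjusted OAC-versus-unexposed hazard ratio of objective 3, and DOAC versus unexposed with a 95% CI, are not planned

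*SAP*

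**What the plan says.** SAP 8.2 defines the two groups in objective 2, "To describe the characteristics of non-valvular AF patients exposed and unexposed to OAC", and objective 3 then reads "To compare the incidence rate of stroke, major bleeding, and death between those two populations".

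SAP 9.7.4.2 gives the Cox analysis the same purpose: "Survival analysis will be performed to compare incidence rate (stroke, major bleeding or death) in AF incident patients exposed and unexposed to OAC therapy". The exposure coding is then set as follows.

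- First model: "patient exposure will be modelled according to five categories: exposure to apixaban, dabigatran or rivaroxaban, exposure to VKA or unexposed patients".
- Second model: "In a second model, exposure to DOACs will be integrated instead of exposure to apixaban, dabigatran or rivaroxaban", which leaves three levels (DOAC, VKA, unexposed).
- Reference level: "For both models, the reference for comparison will be VKA exposure".
- High thromboembolic risk subgroup, DOAC, VKA and unexposed: "The reference for comparison will also be VKA exposure".

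Protocol 3.7.2.2 also names VKA as the reference. The shells follow suit. Tables A10 and A11 mark VKA as the reference row and give crude and adjusted hazard ratios with 95% CIs for the other rows, including one for unexposed time, which the table note defines: "Unexposed to OAC correspond to the period where the patients are not exposed to OAC". Neither table has a row for all OACs pooled. Table A2, which serves the primary objective, does have pooled exposed and unexposed rows.

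**The concern.** The contrast named in the objective differs from the contrasts tabulated. Objective 3 asks about anticoagulated versus non-anticoagulated patients. The tables answer how DOACs, and the absence of treatment, each compare with VKA. VKA is only one part of the exposed group, so unexposed versus VKA is not the overall exposed-versus-unexposed effect. The DOAC part of that comparison has no row of its own.

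This matters because both documents justify the study mainly by the lack of safety data in unexposed patients (SAP 7.2, Protocol 2.1). If the shells are filled as drawn, the report will hold no adjusted overall estimate for that comparison. Readers wanting DOAC versus unexposed would have to divide two hazard ratios and would have no valid adjusted interval for the result.

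**Working it through.** The plan states no event count, power or precision figure for this analysis, so there is nothing to reproduce. The check is which contrasts the planned coding delivers.

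**Step 1. What the output identifies.** With VKA as reference, let b_U be the log hazard ratio of unexposed versus VKA and b_D that of DOAC versus VKA.

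| Contrast | From the tabulated adjusted output | Interval available? |
|---|---|---|
| Unexposed vs VKA | exp(b_U), reported | Yes |
| VKA vs unexposed | exp(−b_U) | Yes, by inverting the limits |
| DOAC vs unexposed | exp(b_D − b_U) | No; needs Var(b_D) + Var(b_U) − 2 Cov(b_D, b_U), and the covariance is not tabulated |
| Any OAC vs unexposed | Not determined by the tabulated hazard ratios | No |

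**Step 2. Illustration of the last two rows.** All inputs are assumptions: rates per person-year of 0.030 (VKA), 0.020 (DOAC) and 0.040 (unexposed), with 100,000 exposed and 40,000 unexposed person-years. Crude rate ratios stand in for hazard ratios.

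- The planned rows would show DOAC vs VKA = 0.020/0.030 = 0.667 and unexposed vs VKA = 0.040/0.030 = 1.333. Hence DOAC vs unexposed = 0.667/1.333 = 0.500.
- With VKA at 10% of exposed time, events are 300 (VKA), 1,800 (DOAC) and 1,600 (unexposed). The covariance of b_D and b_U is 1/300, from the shared reference group.
- With the covariance, the variance is 1/1,800 + 1/1,600 = 0.00118 and the 95% CI is 0.467 to 0.535.
- Ignoring it, the variance is 1/1,800 + 1/1,600 + 2/300 = 0.00785 and the CI is 0.420 to 0.595, which is too wide.
- Pooled any OAC vs unexposed depends on the VKA share of exposed time. At 10% it is (0.1 × 0.030 + 0.9 × 0.020)/0.040 = 0.525; at 30% it is 0.575; at 50% it is 0.625. The two tabulated hazard ratios are the same in all three cases.

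**Step 3. Precision.** Assume 5,000 unexposed and 10,000 exposed events, and approximate the standard error of a log hazard ratio by sqrt(1/a + 1/b), where a and b are the event counts. Unexposed versus any OAC gives sqrt(1/5,000 + 1/10,000) = 0.0173.

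| VKA share of exposed events | VKA events | SE, unexposed vs VKA | Ratio to 0.0173 |
|---|---|---|---|
| 10% | 1,000 | 0.0346 | 2.00 |
| 15% | 1,500 | 0.0294 | 1.70 |
| 30% | 3,000 | 0.0231 | 1.33 |
| 50% | 5,000 | 0.0200 | 1.15 |

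The direction is the same throughout; the size depends on a share that the documents do not give.

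**The case against.** The strongest reply is that the gap is narrow. Unexposed is a level in every model, and Tables A10 and A11 report its hazard ratio against VKA, itself an OAC, with a crude and an adjusted 95% CI for each event. A reader might infer from the single reference level that exposed and unexposed are never compared, or that objective 3 gets no estimate or interval. The shells do not support that.

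Crude figures can also be assembled. Table A2 gives events and person-years for the pooled exposed and unexposed rows, so a crude pooled rate ratio with an approximate interval can be formed. The event counts in Table A10 likewise allow an approximate crude interval for DOAC versus unexposed. This stands, but only for crude figures. SAP 9.7.3.1 makes Table A2 descriptive, with standardisation of the unexposed rates on age alone and no planned ratio. The covariance problem remains for the adjusted intervals.

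VKA as reference is also pre-specified consistently in both documents, and changing the reference level does not alter the fitted model. Keeping agents separate is defensible, since a pooled hazard ratio averages over them. That supports retaining the VKA-referenced rows; it does not supply the contrast the objective names.

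Finally, precision is a secondary matter. SAP 9.5 expects about 1.3 million exposed patients over 2016-2020. Even the assumed standard error of 0.0294 gives limits of about ±6% (exp(1.96 × 0.0294) = 1.06).

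**Conclusion.** The point holds in a limited form. Unexposed versus VKA is the only exposed-versus-unexposed hazard ratio the plan reports directly. The adjusted any-OAC-versus-unexposed contrast of objective 3 is not planned. Neither are the adjusted DOAC-versus-unexposed contrasts with 95% CIs, and those adjusted intervals cannot be rebuilt from the shells. This conclusion rests on the text of SAP 8.2 and 9.7.4.2 and on Tables A10 and A11, not on any assumed number.

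The loss of precision from relying on VKA alone is a factor of about 1.15 to 2.00 in the standard error, under the assumed event counts and VKA shares of 50% down to 10%. No single value in that range can be taken from the documents.

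A reader might also infer that VKA is a poor comparator because of selective prescribing after 2017. SAP 7.1 says only that VKAs were the reference drugs until 2017 and that DOACs could also be used first-line after the 2018 update. It does not say who went on receiving VKA, so the documents do not establish that claim and the point does not depend on it.

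**What to change.** Keep the VKA-referenced results as planned, and add to SAP 9.7.4.2:

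1. For each event, one Cox model with a two-level time-dependent exposure, any OAC versus unexposed, with unexposed as reference. Report crude and adjusted hazard ratios with 95% CIs, using the first-event definition and covariates already specified.
2. From the existing models, contrasts of DOAC and of each DOAC versus unexposed, with 95% CIs, as extra rows in Tables A10 and A11. A contrast statement or a refit with unexposed as reference gives these directly. VKA versus unexposed is the inverse of a row already there and can be shown for completeness.

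The sensitivity versions of Table A10 should carry the same rows. If the sponsor does not want a pooled OAC estimate, objective 3 should instead be reworded to name the contrasts that will be reported.

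The cost is one extra model specification and some contrast statements on the same data set, with no new data or derived variables beyond collapsing the exposure levels.
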